- All other non-hematologic toxicity (except for alopecia) must have resolved to \leq Grade 1 or to the patient's baseline condition

If the patient fails to meet the above-cited criteria for initiation of the next cycle of treatment, dosing should be delayed for 1 week. At the end of that time, the patient should be re-evaluated to determine whether the criteria have been met. If the patient continues to fail to meet the above-cited criteria, delay therapy and continue to reevaluate. The maximum delay before treatment should be discontinued will be 3 weeks or at the discretion of the Principal Investigator. Any delay greater than 21 days must be reviewed with the Lead Principal Investigator if the treating investigator believes that continued treatment is in the subject's best interest and confirmation of clinical benefit (absence of disease progression).

The following tables outline dosing recommendations for Ixazomib, lenalidomide and Dexamethasone.

Dosage adjustments for hematologic toxicity are outlined in Table 6-5

Table 7-5 Ixazomib and Lenalidomide Dose Adjustments for Hematologic Toxicities^{a, b}

Criteria	Action
If platelet count decreased to Grade 3 with clinically significant bleeding or Grade 4 $< 25 \times 10^9/L$ on any dosing day (other than Day 1)	
 • Ixazomib dose and lenalidomide should be withheld. • Complete blood count (CBC) with differential should be repeated at least twice weekly until the platelet counts have exceeded the pre-specified values (see Section 6.3.1) on at least 2 occasions. • Once resolved to Grade ≤ 1: 
 ○ 1st occurrence – decrease lenalidomide by 1 dose level; ixazomib may be reinitiated without dose reduction on the first occurrence. ○ 2nd occurrence - decrease ixazomib 1 dose level and resume len at its most recent dose ○ 3rd occurrence – decrease len 1 dose level from previous dose ○ 4th occurrence – decrease ixazomib 1 dose level from previous dose
Within-Cycle Dose Modifications	
Day 1 of Cycle Dose Modifications	
 • 1st occurrence – decrease lenalidomide 1 dose level • 2nd occurrence – decrease ixazomib 1 dose level • 3rd occurrence – decrease lenalidomide by 1 additional dose level • 4th occurrence – decrease ixazomib by 1 additional dose level
Neutrophil count (ANC) decreased Grade 3 (ANC 500-1000/mm ³) or > Grade 3 with fever (temperature $>38.5^{\circ}\text{C}$)	

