Dosage adjustments for hematologic toxicity are outlined in Table 6-5

Table 7-5 Ixazomib and Lenalidomide Dose Adjustments for Hematologic Toxicities^{a, b}

Criteria	Action
Within-Cycle Dose Modifications	
 • Ixazomib dose and lenalidomide should be withheld. • Complete blood count (CBC) with differential should be repeated at least twice weekly until the ANC has exceeded the pre-specified values (see Section 6.3.1) on at least 2 occasions. • If neutropenia resolved to <Grade 2: 
 ◦ Lenalidomide decrease 1 dose level ◦ Ixazomib – resume at its most recent dose if ANC recovered prior to next planned dose and resume planned treatment cycle
Day 1 of Cycle Dose Modifications	
 • If neutropenia is the only toxicity for which a dose reduction is required, G-CSF may be used prophylactically, as per ASCO guidelines, for the subsequent cycle and dose maintained • For each subsequent occurrence of the same level of neutrophil count decrease, hold lenalidomide treatment and upon recovery of ANC to >1,000/mm³ resume as follows: 
 ◦ 1st occurrence – decrease lenalidomide 1 dose level ◦ 2nd occurrence – decrease ixazomib 1 dose level ◦ 3rd occurrence – decrease lenalidomide by 1 additional dose level; do not dose below 5mg daily
Grade 4 neutropenia (<500/mm³)	
Within Cycle Dose Modifications	
 • Ixazomib dose and lenalidomide should be withheld. • Complete blood count (CBC) with differential should be repeated at least twice weekly • If neutropenia resolved to <Grade 2 within the cycle: 
 ◦ Lenalidomide decrease 1 dose level below current dose level ◦ Ixazomib if prior to next planned dose, decrease 1 dose level

Dosage adjustments for hematologic toxicity are outlined in Table 6-5

Table 7-5 Ixazomib and Lenalidomide Dose Adjustments for Hematologic Toxicities^{a, b}

Criteria	Action
Day 1 of Cycle Dose Modifications	
 • Use of G-CSF as above • For each subsequent drop $<1,000/\text{mm}^3$ and recovery to $>1,000/\text{mm}^3$, decrease lenalidomide one dose level less than the previous dose, but do not dose below 5 mg daily

a) Both drugs may be reduced at the same time at the investigator's discretion
b) Doses held during a treatment cycle are not to be replaced

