Allergic Reaction / Hypersensitivity	
 Grade 2-3 Grade 4 
 Hold Lenalidomide, follow at least weekly. If the toxicity resolves to \leq Grade 1 prior to Day 21, restart at 1 dose decrement and continue the cycle until Day 21. Discontinue lenalidomide treatment
Infection Grade 3-4	Hold lenalidomide, ixazomib, and dexamethasone until systemic treatment for infection is completed. If no neutropenia, restart all three drugs at same dose. If neutropenic, follow neutropenic instructions.
Herpes Zoster or simplex of any grade	Hold Lenalidomide, ixazomib, and dexamethasone until lesions are dry. Resume at same doses.
Renal Dysfunction	Dose reduce per lenalidomide package insert for impaired renal function; monitor renal function regularly
Venous Thrombosis/Embolism \geq Grade 3	Hold lenalidomide dose and adjust anticoagulation regimen; re-start at Treating Investigator's discretion at same dose
Hyperthyroidism or hypothyroidism	Omit lenalidomide for remainder of cycle, evaluate, and initiate appropriate therapy. Restart lenalidomide next cycle at 1 dose decrement
Congestive heart failure (CHF)	Any subject with NYHA stage III or IV CHF, whether or not lenalidomide related, must have the dose held until resolution or return to baseline. If CHF was felt to be lenalidomide related, reinstate by one dose decrement after return to baseline. If no resolution of CHF after 2 weeks, the subject will be withdrawn from the study.

Table 7-8 Treatment Guidelines for Toxicity Related to Dexamethasone

Body System	Symptom	Recommended Action
Gastrointestinal	Dyspepsia, gastric or duodenal ulcer, gastritis Grade 1-2 (requiring medical management)	Treat with H ₂ blockers, sucralfate, or omeprazole. If symptoms persist despite above measures, decrease dexamethasone dose by 1 dose level.
Gastrointestinal	≥ Grade 3 (requiring hospitalization or surgery)	Hold dexamethasone until symptoms adequately controlled. Restart at 1 dose decrement along with concurrent therapy with H ₂ blockers, sucralfate, or omeprazole. If symptoms persist despite above measures, discontinue dexamethasone permanently.
Gastrointestinal	Acute pancreatitis	Discontinue dexamethasone permanently.

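### Grade 4 neutropenia with fever meets two rows of Table 7-5, and the two rows give incompatible within-cycle instructions for restarting ixazomib

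*Combined protocol and SAP*

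**What the plan says.** Table 7-5 in Section 7.3.1 has two neutropenia rows, each with within-cycle and Day 1 instructions.

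- **First row.** The criterion is "Neutrophil count (ANC) decreased Grade 3 (ANC 500-1000/mm ³) or > Grade 3 with fever", with fever defined as a temperature above 38.5 °C. Within the cycle, once neutropenia has resolved to below Grade 2, lenalidomide goes down one level. The ixazomib line reads "Ixazomib – resume at its most recent dose if ANC recovered prior to next planned dose and resume planned treatment cycle".
- **Second row.** The criterion is "Grade 4 neutropenia (<500/mm³"), and fever is not mentioned. Within the cycle, after the same resolution, the lenalidomide line is "Lenalidomide decrease 1 dose level below current dose level" and the ixazomib line is "Ixazomib if prior to next planned dose, decrease 1 dose level".

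The Day 1 instructions also differ. The first row has a ladder for later occurrences of the same level of decrease: lenalidomide is lowered at the 1st, ixazomib at the 2nd and lenalidomide again at the 3rd. For each later fall below 1,000/mm³, the Grade 4 row says only to "decrease lenalidomide one dose level less than the previous dose, but do not dose below 5 mg daily".

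Four other places bear on the question:
- Footnote a to Table 7-5 lets the investigator reduce both drugs at once.
- Section 7.3 sends modifications that differ from the protocol to the Lead Principal Investigator.
- The infection row of Table 7-7 (Grade 3-4) says "If neutropenic, follow neutropenic instructions".
- The neutropenia paragraph of Section 7.6 permits restarting at a reduced level once ANC recovers.

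The text after Table 7-6 bars re-escalation of any drug reduced for toxicity.

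**The concern.** A dose-modification table should return one action for each event. Here an event at the severe end of the neutropenia scale returns two, and a site cannot follow both. If the first row is taken to govern, the febrile patient restarts ixazomib unchanged while a patient with the same ANC and no fever restarts one level lower. That ordering is hard to read as intended, and nothing in the protocol explains it.

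The stakes are safety and consistency. Enrollment is planned across 8 centers (Section 4.4), and two sites could treat the same event differently while each complies with the table. Because re-escalation is not allowed, the choice of row fixes the ceiling on that patient's ixazomib dose for the remaining cycles. Only the IRd arm is exposed, since control patients receive no ixazomib.

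**Working it through.** No plan figure needs to be reproduced. The check applies the two criteria to each combination of grade and fever and reads off the within-cycle ixazomib action.

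| Event | Meets first row? | Meets Grade 4 row? | Within-cycle ixazomib action on restart |
|---|---|---|---|
| Grade 3, no fever | Yes | No | Most recent dose |
| Grade 3, fever | Yes | No | Most recent dose |
| Grade 4, no fever | No | Yes | One level lower |
| Grade 4, fever | Yes | Yes | Most recent dose **and** one level lower |

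Only the last case has two answers.

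**Does the overlap depend on how the first criterion is read?** There are three possible readings: the sign as printed; the sign as a lost at-least sign; and the fever qualifier attached to both halves of the criterion. Grade 4 with fever satisfies the first row under all three, and it always satisfies the second.

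**Is it an artefact of the table breaking across a page?** No. The actions that follow the first criterion refer to ANC and neutropenia, and they come before the Grade 4 heading, so the pairing of criterion and action is sound.

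**What do the rows share?** Both withhold ixazomib and lenalidomide, both repeat the blood count at least twice weekly, both wait for resolution to below Grade 2, and both lower lenalidomide one level. The incompatibility is confined to the ixazomib restart level within the cycle.

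**Does any other text set precedence?**
- Footnote a allows both drugs to be reduced but does not say which row governs.
- Section 7.3 sends departures from the stated modifications to the Lead Principal Investigator. Both actions are stated here, so following either is not a departure and triggers no call.
- The infection row of Table 7-7 leads back to the same two rows.
- Section 7.6 is permissive and does not choose between the rows.

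**Repeated events.** Take a patient with a Grade 4 event followed by several Day 1 ANC values of 500-1000/mm³. Under the Grade 4 row each later fall lowers lenalidomide only. Under the first row's ladder the 2nd occurrence lowers ixazomib instead. The paths separate at the second or third such value, depending on whether the first value in that band counts as the 1st occurrence or as the initial event at that level. The table does not say.

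**The case against.** The strongest reply is that the difference is narrow and the protocol leaves room for judgement. The two rows agree on everything except the ixazomib restart level. Section 7.3.1 is headed as recommended criteria, footnote a and Section 7.6 both allow a reduced restart, and the Lead Principal Investigator can be consulted. No text forces the milder action on a febrile patient. All of this stands, and it limits the practical harm. It does not say which row applies, so the contradiction remains.

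A reader might infer three stronger conclusions. The documents support none of them.

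- **That the row chosen decides whether a patient loses ixazomib.** Table 7-1 gives a patient on 3 mg one step (2.3 mg) before discontinuation, so two reductions would end the drug. But this needs both events to be handled under the Grade 4 row's within-cycle line, because that row's Day 1 text lowers lenalidomide only. Nor is the dose guaranteed to stay at 3 mg under the first row, whose own ladder lowers ixazomib at a 2nd occurrence. Over repeated events the first row can be the stricter one for ixazomib. The outcome depends on how occurrences are counted.
- **That the Day 1 instructions conflict from the first Grade 3 value after a Grade 4 event.** The first row's ladder concerns the same level of decrease, and its 1st occurrence lowers lenalidomide, as the Grade 4 row does. Divergence needs repeated events.
- **That the primary endpoint is materially affected.** The synopsis ends protocol treatment if ixazomib is permanently stopped for intolerance, and Section 8.1.4 counts early discontinuation as failure, so a route exists. The numbers along it are small. Table 1-3 gives neutropenia of any grade in 43/173 = 25%, or 0.25 × 30 = 7.5 IRd patients. The documents give no febrile Grade 4 share. Assuming 5-20% of these gives 0.4-1.5 patients with such an event, and discontinuation needs two reductions from 3 mg or three from 4 mg. At 26.7% versus 5% with 30 per arm and a one-sided 10% Fisher test, turning one IRd responder into a failure reverses a positive result in about 10.4% of trials. For an IRd patient chosen at random the figure is about 2.3%, before multiplying by the chance of enough events to stop ixazomib.

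**Conclusion.** The contradiction is real and sits in the current text. Febrile Grade 4 neutropenia meets both neutropenia rows of Table 7-5, the within-cycle ixazomib actions cannot both be followed, and no other provision decides between them. If the first row governs, fever brings a milder within-cycle ixazomib action at the same ANC.

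The point is limited to the IRd arm and to the ixazomib restart level. It rests on the wording of the table alone, with no numerical assumption. Few patients are likely to be affected, although the documents do not allow a firm count. It matters for patient safety and for consistent dosing between sites. No material effect on the primary endpoint is claimed. Counting of occurrences on Day 1 after a Grade 4 event is a related ambiguity to settle at the same time, not a second established contradiction.

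**What to change.** Reword the two neutropenia rows of Table 7-5 so that each event meets only one of them, and state explicitly which row covers Grade 4 with fever. The action for that event is for the sponsor's clinicians to choose; the statistical request is only that the table return a single instruction.

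In the same edit, state how occurrences are counted when ANC values of 500-1000/mm³ recur after a Grade 4 event, and whether the first row's ladder or the Grade 4 row's Day 1 text applies to them. Once the rows are mutually exclusive, the infection row of Table 7-7 will point to one instruction without further change.

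The cost is the wording of two table rows in the next amendment. Sample size, analysis and data collection are unaffected.

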7.3 Dose-Modification Guidelines

The following sections summarize dosing modifications for ixazomib, lenalidomide, and dexamethasone. Dose modifications different from those stated in the protocol must be discussed with the Lead Principal Investigator. Administration of ixazomib and/or lenalidomide will be discontinued in the event of any toxicity that, in the opinion of the Lead or Treating Investigator, warrants discontinuation.

In addition to dose reductions, administration of ixazomib and/or lenalidomide will be held temporarily in the event of a treatment-related toxicity, at the Treating Investigator's discretion. Study treatment may be re-introduced, if the event resolves back to the patient's baseline value or to \leq Grade 1 within 21 days; otherwise, study drug will be permanently discontinued. Any deviations from this plan must be approved by the Lead Principal Investigator.

Experimental Arm:

Table 7-1 Ixazomib Dose Adjustments

Nominal Ixazomib Dose	Dose -1	Dose -2	Dose -3
4 mg Days 1, 8, 15 (if escalated after Cycle 1)	3 mg	2.3 mg	Discontinue
3 mg Days 1,8,15	2.3mg	Discontinue	N/A

Table 7-2 Lenalidomide Dose Adjustments

Nominal Lenalidomide Dose	Dose -1	Dose -2	Dose -3	Dose -4	Dose -5
25 mg Days 1-21	20mg	15 mg	10 mg	5 mg	5 mg every other day

15 mg Days 1-21	10 mg	5 mg	5 mg every other day	Discontinue	N/A
1 mg Days 1-21	5 mg	5 mg every other day	Discontinue	N/A	N/A

Table 7-3 Dexamethasone Dose Adjustments*

Nominal Dexamethasone Dose	Dose -1	Dose -2	Dose -3	Dose -4
40 mg	20 mg	12 mg	8 mg	4 mg

*Split dosing of dexamethasone on days 1, 2, 8, 9, 15, 16, 22, and 23 may be implemented to control toxicities that do not require a dose reduction. Split dosing requires Lead Principal Investigator approval before implementing

Control Arm

Table 7-4 Lenalidomide Dose Adjustments

Nominal Lenalidomide Dose	Dose -1	Dose -2	Dose -3	Dose -4
15 mg Days 1-28	10 mg	5 mg	5 mg Days 1-21	5 mg every other day Days 1-21
10 mg Days 1-28	5 mg	5 mg Days 1-21	5 mg every other day Days 1-21	Discontinue

7.3.1 Recommended Criteria for Beginning or Delaying a Subsequent Treatment Cycle & Dose Modifications for Treatment Associated Toxicity

All treatment cycles are 28 days. For a new cycle of treatment to begin, the patient must meet the following criteria:

- ANC must be $\geq 1,000/\text{mm}^3$.
- Platelet count must be $\geq 75,000/\text{mm}^3$.

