Treatment modifications due to ixazomib-related AEs are outlined in Table 6-6.

Table 7-6 Ixazomib Treatment Modification (Delays, Reductions, and Discontinuations) Due to Adverse Events (Non-Hematologic Toxicities)

Adverse Event (Severity)	Action on ixazomib	Further Considerations
Peripheral Neuropathy:		
Grade 1 peripheral neuropathy without pain	
 • No action 	Grade 1 signs and symptoms: asymptomatic; without pain or loss of function; clinical or diagnostic observations only [14]
New or worsening Grade 1 peripheral neuropathy with pain or Grade 2	
 • Hold ixazomib until resolution to Grade ≤ 1 without pain or baseline • Reduce ixazomib 1 dose level 	Grade 2 signs and symptoms: Moderate symptoms; limiting instrumental activities of daily living (ADL) [14]
New or worsening Grade 2 peripheral neuropathy with pain or Grade 3	
 • Hold ixazomib until resolution to Grade ≤ 1 without pain or baseline • Reduce ixazomib to next lower dose upon recovery 	Grade 3 signs and symptoms: severe symptoms; limiting self-care ADL; assistive device indicated [14]
New or worsening Grade 4 peripheral neuropathy	
 • Discontinue ixazomib 	

Table 7-6 Ixazomib Treatment Modification (Delays, Reductions, and Discontinuations) Due to Adverse Events (Non-Hematologic Toxicities)

Adverse Event (Severity)	Action on ixazomib	Further Considerations
Grade 2 Rash	
 Follow at least weekly Symptomatic recommendations as per section 6.6 	The investigator and project clinician may discuss considerations for dose modifications and symptom management.
Grade 3 non-hematologic toxicity judged to be related to ixazomib except for the following toxicity: 
 > Grade 3 nausea and/or emesis in the absence of optimal anti-emetic prophylaxis (section 6.7) > Grade 3 diarrhea that occurs in the absence of optimal supportive therapy (section 6.7) Grade 3 fatigue 	
 Hold ixazomib until resolution to Grade < 1 or baseline 
Subsequent recurrence Grade 3 that does not recover to < Grade 1 reduce ixazomib 1 dose level
	Symptomatic recommendations noted in Section 6.7 Monitor closely, take appropriate medical precautions, and provide appropriate symptomatic care

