Symptomatic measures such as antihistamines or corticosteroids (oral or topical) have been successfully used to manage rash and have been used prophylactically in subsequent cycles. The use of a topical, IV, or oral steroid (e.g., prednisone \leq 10 mg per day or equivalent) is permitted. Management of a Grade 3 rash may require intravenous antihistamines or corticosteroids. Administration of ixazomib (and/or other causative agent if given in combination) should be modified per protocol and re-initiated at a reduced level from where rash was noted (also, per protocol).

In line with clinical practice, dermatology consult and biopsy of Grade 3 or higher rash or any SAE involving rash is recommended. Prophylactic measures should also be considered if a

patient has previously developed a rash (e.g., using a thick, alcohol-free emollient cream on dry areas of the body or oral or topical antihistamines). A rare risk is Stevens – Johnson Syndrome, a severe and potentially life-threatening rash with skin peeling and mouth sores, which should be managed symptomatically according to standard medical practice. Punch biopsies for histopathological analysis are encouraged at the discretion of the investigator.

Thrombocytopenia

Blood counts should be monitored regularly as outlined in the protocol with additional testing obtained according to standard clinical practice. Thrombocytopenia may be severe but has been manageable with platelet transfusions according to standard clinical practice. Ixazomib administration should be modified as noted as per dose modification recommendations in the protocol when thrombocytopenia occurs (see Table 6-2). Therapy can be reinitiated at a reduced level upon recovery of platelet counts. A rare risk is thrombotic thrombocytopenic purpura (TTP), a rare blood disorder where blood clots form in small blood vessels throughout the body characterized by thrombocytopenia, petechiae, fever, or possibly more serious signs and symptoms. TTP should be managed symptomatically according to standard medical practice.

Neutropenia

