patient is rendered non-evaluable, a new patient will be randomized into the trial to preserve the sample size for primary endpoint analysis. Patients enrolled in this trial will be patients who completed initial induction followed by autologous stem cell transplant for symptomatic myeloma (per IMWG criteria) and in the first 0-6 months of Lenalidomide maintenance provided that was initiated within 6 months after transplant as per standard of care and with at least MRD-positive residual myeloma. The study's primary endpoint, attainment of MRD-negative disease by MFC will be assessed at the completion of the 12 cycle of protocol treatment (both arms). In patients that were enrolled based on their MRD-positivity by MFC, an improvement will be counted when these patients switch to MRD-negative disease by MFC at the 12-month time-point. Patients that were enrolled per their MRD-positivity by NGS will require NGS analysis to determine their MRD status at 12 months of treatment. In this patient population, only a switch from MRD-positivity to negativity by NGS will be counted as an improvement. We anticipate that no more than 10% of patients will be enrolled who are MFC negative but NGS positive. If there is an imbalance between the two treatment arms in this variable we will adjust by post-hoc stratification or covariate analysis. All patients enrolled and receiving any IRD or R treatment will be evaluable for this endpoint, with the exception of patients that decline to receive treatment for reasons unrelated to toxicity and/or efficacy. Patients in that category will be replaced. All other patients who discontinue treatment before receiving 12 cycles of protocol treatment will be considered treatment failures for assessment of the study's primary endpoint. The proportion of MRD-negative patients will be reported along with 95% confidence intervals.

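### Table 7-6 ties its only ixazomib reduction for Grade 3 non-hematologic toxicity to a recurrence that has not recovered, which conflicts with its own hold rule and, by default, with the 21-day stop in section 7.3

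*Combined protocol and SAP*

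**What the plan says.** The row of Table 7-6 for Grade 3 non-hematologic toxicity judged related to ixazomib has two instructions. The first is "Hold ixazomib until resolution to Grade < 1 or baseline". The second is a reduction of ixazomib by one dose level, and its condition is worded "Subsequent recurrence Grade 3 that does not recover to" below Grade 1. In full it reads "Subsequent recurrence Grade 3 that does not recover to < Grade 1 reduce ixazomib 1 dose level". The row says nothing else about the dose on restart.

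Section 7.3 sets the general rule. Treatment held for toxicity may be restarted if the event returns to baseline or to Grade 1 or lower "within 21 days; otherwise, study drug will be permanently discontinued". It adds: "Any deviations from this plan must be approved by the Lead Principal Investigator". Section 7.2.1 uses the term study drug for ixazomib capsules.

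On rash, section 7.6 says that administration of ixazomib, or of another causative agent given with it, "should be modified per protocol and re-initiated at a reduced level from where rash was noted", and then defers to the protocol a second time.

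On the primary endpoint, the Populations for Analysis text (8.1.4, which runs on from 8.1.3.2) exempts patients who decline treatment for reasons unrelated to toxicity or efficacy. It then says: "All other patients who discontinue treatment before receiving 12 cycles of protocol treatment will be considered treatment failures".

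**The concern.** A hold-and-modify rule has to tell a site what to do in three situations: a first event, a recurrence that recovers, and a recurrence that does not. This row gives a clear hold for the first, no restart dose for the second, and instructions for the third that cannot both be carried out at once. The reduction is attached to the one patient who, under the same row, should not be receiving the drug.

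The handling of ixazomib toxicity feeds into the endpoint. The Duration of Study text in the Protocol Summary ends protocol treatment when lenalidomide and/or ixazomib is permanently stopped for intolerance, and 8.1.4 counts a stop before 12 cycles as a failure. Only the IRd arm receives ixazomib, so any variation between sites in reading this row acts on one arm only.

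**Working it through.** No formula applies. The check sets the row beside the other rules and takes each case in turn. The one figure that can be compared agrees: the 3-week maximum delay in section 7.3.1 is 3 × 7 = 21 days, as in sections 7.3 and 7.10.

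First, read the symbol in the row as Grade 1 or lower:

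| Case | Table 7-6, Grade 3 row | Other text |
|---|---|---|
| First event, recovers | Hold; no reduction stated | 7.3 permits restart; 7.6 (rash) speaks of a reduced level, per protocol |
| Recurrence, recovers | Hold; the condition for reduction is not met, so none is stated | 7.3 permits restart; 7.6 as above for rash |
| Recurrence, not recovered, up to 21 days | Hold, and also reduce one level | 7.3 and the new-cycle criteria in 7.3.1 do not permit restart yet |
| Recurrence, not recovered, beyond 21 days | Hold, and also reduce one level | 7.3: permanent stop by default; 7.3, 7.3.1, the delay row of Table 7-6 and 7.10 allow an exception through the lead or overall investigator |

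On this reading, no default route leads to a reduced dose for the patient whom the reduction clause describes. It becomes possible only through the override.

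Second, read the symbol literally as below Grade 1. A recurrence that settles at Grade 1 has not met the row's target, but section 7.3 allows restart at Grade 1. The reduction clause then has a patient to apply to, and the 21-day conflict disappears for that patient. Two problems remain. The row's hold rule still says to wait for below Grade 1 or baseline, so it contradicts the reduction unless the patient's baseline is Grade 1. A recurrence that recovers fully still has no reduction stated. A recurrence that stays at Grade 2 or 3 is as in the table above.

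Third, compare rows that cover similar events:

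- Table 7-6, neuropathy Grade 2 with pain or Grade 3: hold until recovery, then reduce on recovery.
- Table 7-6, cycle start delayed by more than 2 weeks for ixazomib toxicity: hold until resolution and reduce one level.
- Table 7-5, platelets: a numbered action for each occurrence, once resolved.
- Table 7-7, lenalidomide, other Grade 3/4 toxicities: hold until resolved, then restart at the next lower level.

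In each of these the reduction follows recovery. The Grade 3 row is the only one of the five that attaches it to non-recovery. The comparison shows that the row is inconsistent with its neighbours; it does not show which action is clinically right.

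On size, section 1.3 gives rash of about 50% and, in combination trials, diarrhea of 47%. Both are all-grade. The documents give no Grade 3 rate, no recurrence rate and no rate of non-recovery, so a count of affected patients cannot be derived. For scale only, one patient in 30 is 1/30 = 3.3 percentage points of the IRd rate. That shift occurs only if the patient would otherwise have been MRD-negative at 12 months.

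**The case against.** The strongest reply is that the instructions can be read as a sequence: hold, resume lower after recovery, stop at 21 days. Other rows of the table pair a hold with a reduction in that way, and naming a lower dose does not permit giving it early. This is a reasonable guess at the intent. It is not what the clause says, since its condition is non-recovery, and it still supplies no action for a recurrence that recovers.

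A reader might infer that the protocol allows dosing into unresolved Grade 3 toxicity. The documents do not support that. The row's own hold, the restart condition in section 7.3 and the new-cycle criteria in section 7.3.1 all stand against it.

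A reader might also infer unlimited rechallenge at the same dose. That treats silence in one row as permission. Section 7.2 asks for doses to be modified to patient tolerance, section 7.3 requires discontinuation for any toxicity that the lead or treating investigator judges to warrant it, and the delay row reduces after more than 2 weeks. Section 7.3.1.1 implies a reduction for Grade 3 gastrointestinal toxicity or fatigue that persists beyond set times.

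Three further points stand. The 21-day stop is a default that can be overridden. The rash sentence also covers other causative agents and defers to the protocol, and Table 7-7 does reduce lenalidomide after a resolved Grade 3 non-blistering rash, so 7.6 is in tension with the row and not in flat contradiction. Finally, section 7.10 requires contact with the Lead Principal Investigator before a withdrawal, which dampens variation between sites.

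**Conclusion.** The point holds in a limited form. The Grade 3 row contradicts its own hold rule, conflicts by default with the 21-day stop in section 7.3, and states no reduction for a recurrence that recovers. The contradiction with the hold rule survives either reading of the symbol, except where the patient's baseline is Grade 1. The 21-day conflict is eased on the literal reading and is subject to the Lead Principal Investigator's approval. The printed symbol may itself be a text-extraction loss.

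The consequence is that sites may treat the same IRd-arm event differently and that a few patients' endpoint status could turn on it. The number is probably small: the stop-or-reduce conflict needs a Grade 3 event that recurs and also fails to recover, and the row and section 7.3.1.1 exempt several common events. Applying an assumed Grade 3 rate to the 30 IRd patients would overstate it, because that counts every Grade 3 event. Sample size and the primary test are unaffected. It is worth correcting because it bears on safety and the correction is simple.

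**What to change.** Reconcile the Grade 3 row of Table 7-6 with sections 7.3 and 7.3.1 and with the rash text in 7.6. A first event, a recurrence that recovers and a recurrence that does not recover should each have one action, and no case should carry both a hold and a dose. Print the recovery grade unambiguously and use the same one in the row and in 7.3. State which section prevails, and how the Lead Principal Investigator override applies after 21 days. The choice of action belongs to the sponsor's clinicians and is not proposed here.

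The cost is one table row and a few cross-references in a protocol amendment, with the ethics approvals that section 12.6 requires. No visit, sample or analysis changes.
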